# **Document History**

| Version | Date                       | Author   | Comments/Change Details   |
|---------|----------------------------|--|---|
| 1.0     | 6 th June 2019  | [name] (Clinical
Trials Unit, University of
Exeter) | Finalised version of
Statistical Analysis Plan
(including Economic
Analysis)       |
| 1.1     | 7 th June 2019  | [name] (Clinical
Trials Unit, University of
Exeter) | Updated to include detail
under Section 8 - Health
economic analysis plan             |
| 1.2     | 28 th June 2019 | [name] (Clinical
Trials Unit, University of
Exeter) | Insertion of front cover,
table of contents. Minor
formatting changes                 |
| 1.3     | 17 December
2020        | [name] (Clinical
Trials Unit, University of
Exeter) | Amendments related to
effects of COVID-19 on
mental health during the
trial period |

| 1.4 | 18/03/2021 | [name] (Clinical
Trials Unit, University of
Exeter) | Definition of window of
opportunity to provide
outcome data using link |
|-----|------------|--|--|
| 1.5 | 17/06/2021 | [name] (Clinical
Trials Unit, University of
Exeter) | Strategies to address app
outage  |
| 1.6 | 24/06/2021 | [name] (Clinical
Trials Unit, University of
Exeter) | Strategies to address app
outage  |

## **ECoWeB Statistical Analysis plan**

This Statistical Analysis Plan (SAP) was finalised on 06 June 2019; version number 1.0.

## 1. Administrative information

#### 1.1 Trial title and trial registration

The full title of the trial is "Assessing and Enhancing Emotional Competence for Well-Being (ECoWeB) in Young Adults: A principled, evidence-based, mobile-health approach to prevent mental disorders and promote mental well-being". The trial registration number is: **ISRCTN** NCT04148508. This information is also set out in Table 1.

#### 1.2 Trial roles and responsibilities

Roles and responsibilities for the ECoWeB trial are set out in Table 1

#### 1.3 Preparation of the statistical analysis plan

The SAP has been prepared in accordance with ICH-9 statistical guidelines for clinical trials [1] and JAMA Guidelines for the Content of Statistical Analysis Plans in Clinical Trials [2], and with guidance from the Exeter Clinical Trials Unit (ExeCTU) Standard Operating Procedure (SOP) for Statistical Principles. Results are to be reported in accordance with the CONSORT checklist for trials [3], the CONSORT extension for non-pharmacologic trials [4], and the CONSORT extension for multi-arm trials. [5]

#### 1.4 Statistical analysis plan and trial protocol

This SAP is not intended to be a standalone document and should be used in conjunction with the trial protocol (version 1.3 dated 05/07/2021).

#### 1.5 Statistical analysis plan roles and responsibilities

The roles and responsibilities of those who produced this SAP are set out in Table 2.

#### 1.7 Revisions to the statistical analysis plan

Revisions to this SAP will be set out in Table 4. Revisions can be made at any time during the trial and will be approved by the TMG. Revisions following scrutiny of the data and unblinded interpretation of the analyses will be considered to be post hoc and will require strong justification.

#### Table 4 Statistical Analysis Plan revisions

| SAP revision
number | Date of revision
(DD-MM-YYYY) | Timing of SAP
revision in
relation to trial
progress | Details of the
revision  | Justification for the revision |
|------------------------|----------------------------------|---|---|--------------------------------|
| 1.0                    | 06/06/2019                       | Set-up  |   |                                |
| 1.1                    | 07/06/2019                       | Set-up  | Updated to
include detail
under Section 8 -
Health economic
analysis plan | Inclusion of HEAP              |
| 1.2                    | 28/06/2019                       | Set-up  | Insertion of front cover, table of  | Minor formatting changes.      |

| 1.3 | 17/12/2020 | Participant
recruitment | contents. Minor
formatting
changes
Section 6.7:
Addressing
COVID-19 related
issues
Section 6.8:
Addressing
protocol
violations | Concerns related
to effects of
COVID-19 on
mental wellbeing
were not
addressed in the
original SAP
(written prior to
the COVID-19
pandemic).  |
|-----|------------|----------------------------|--|--|
| 1.4 | 18/03/2021 | Participant
recruitment | Section 6.1 Trial
outcomes
Section 6.3
Analysis methods   | Duration of time
that the link for
submission of
outcome data
collection at each
follow-up
timepoint has
been confirmed
to be just under 3
weeks. This is
now reflected in
the SAP. |
| 1.5 | 17/06/2021 | Participant
recruitment | Section 6.9
Addressing
protocol
violations due to
app outage   | Response to app
outage for ~4
weeks in March
2021.  |
| 1.6 | 24/06/2021 | Participant
recruitment | Section 6.9
Addressing
protocol
violations due to
app outage   | Response to app
outage for ~4
weeks in March
2021.  |

## 2. Trial description

### 2.1 Background and rationale

The ECoWeB project is a multi-country project that aims to develop a personalised self-help app to support mental health and well-being in young adults, and to evaluate the performance of the app against usual practice and an active but non-personalised app intervention; all interventions will include use of the app for self-monitoring. Mental and emotional wellbeing in young adults are known to be associated with mental health disorders, such as anxiety and depression, and to be related to non-health outcomes such as education and employment achievements. The ECoWeB programme incorporates two clinical trials, ECoWeB-PROMOTE and ECoWeB-PREVENT, to be run in parallel. Both trials include the same three interventions and collect the same outcome data. The aim of these trials is to examine the effectiveness of two active forms of psychological self-help delivered by means of an app, both of which are compared with a usual care control group.

#### 2.2 Objectives

Both trials seek to evaluate mental health and emotional wellbeing within their respective participant samples comparing two active interventions (one personalised, one uniform across participants) against usual care (self-monitoring of emotional well-being via an app) and against each other. In addition, a health economic evaluation will be performed (Section 8).

## 3. Study methods

#### 3.1 Trial design

Both PROMOTE and PREVENT are 3-arm parallel group trials, with individual randomisation in a 1:1:1 ratio. For both trials, an external pilot will be carried out to identify any issues in the administrative aspects of the trial, such as participant recruitment, consent procedures for under 18s (in countries where parental consent is required for trial participation of under-18s. The data from this pilot will not be combined with the results of the main trials, which are fully powered definitive trials. Furthermore, the external pilot has no stopping criteria that would, if fulfilled, lead to the main trial being cancelled prior to commencement.

The usual care intervention comprises only self-monitoring using the app. The personalised active intervention consists of usual care plus two out of four modules for emotional competence self-help training, selected for each participant. The standard active intervention consists of usual care plus a self-help intervention based on CBT principles, also delivered via the app.

The ECoWeB trials will be performed within the framework of a cohort multiple RCT (cmRCT). A top level cohort of potential participants, whose eligibility for either PROMOTE or PREVENT has been established, will be recruited. These participants will consent to participating in the cohort and to being offered potential treatments if applicable via the screening website. Based on their baseline scores on eight measures (collected at baseline), to be converted to z-scores (using means and standard deviations derived from a validation study across all four sites), the participant will be allocated to either PROMOTE (lower risk of mental health problems) or PREVENT (higher risk of mental health problems). Full details of the process for allocation of participants to either PROMOTE

or PREVENT are reported elsewhere (Trial selection, randomisation, selection of emotional competence intervention components document).

Following selection of eligible trial, participants will be randomised to one of the three interventions (Section 3.2). Those participants who are allocated to receive the personalised intervention will receive two of the four available modules (Achievement appraisal; Social appraisal; Rumination; Emotion knowledge and Perception), with six module combinations possible. Module selection will be based on the participant's responses to 11 measures across the 4 components - full details are provided elsewhere (Trial selection, randomisation, selection of emotional competence intervention components document).

## 3.2 Trial population

The two trials differ with regard to their target populations. Both trials include young adults aged 16–22 years. The PROMOTE trial will recruit participants who do not indicate potential increased risk of poor mental health at the baseline assessment based on emotional competence scores. The PREVENT trial will recruit participants who indicate potential increased risk for mental illness at the baseline assessment based on emotional competence scores. Both trials will exclude people with a past history of mental health problems, including depression and self-harm, and those with current mental health disorders, including those receiving psychological therapy or psychiatric medication. Full inclusion/exclusion criteria are set out in the trial protocol v.1.3. The aim of these trials is to examine the effectiveness of two active forms of psychological self-help delivered by means of an app, both of which are compared with a usual practice control group. Both trials will be delivered in four countries (UK, Germany, Spain, Belgium), i.e. all participants will be resident in one of these four countries at baseline; within each country, participants will have the option to communicate with the trial (via the trial website that will be used to recruit participants and conduct follow-up assessments and via the app, which will be used for intervention delivery) in one of four languages (English, German, Spanish, Dutch).

#### 3.3 Randomisation

Within both PROMOTE and PREVENT separately, participants will be allocated to one of the three interventions in a 1:1:1 ratio using a minimisation algorithm to promote balance across the arms overall and within minimisation factors. The minimisation factors to be used are gender (categorised as male:female:both:neither anticipated to be recruited in a 20:70:5:5 ratio), age (categorised as 16–17:18–22, anticipated to be recruited in a 20:80 ratio), and country of residence (UK:Germany:Spain:Belgium, anticipated to be recruited in a 28:28:28:18 ratio). The first 50 randomisations (for both trials) will be performed using simple randomisation; subsequent randomisations will use the minimisation algorithm, taking account of the previous allocations. Further details of the randomisation procedure are provided elsewhere (Trial selection, randomisation, selection of emotional competence intervention components document).

Randomisation across all countries will be carried out by ExeCTU. The randomisation algorithm will be automatically invoked when the participant has submitted the required baseline data and provided consent. The participant will be immediately informed of the allocated treatment and the downloaded version of the app will provide the appropriate intervention. There is no possibility for a participant to receive a version of the app other than the version to which the participant was randomly allocated.

## 3.4 Sample size

PROMOTE and PREVENT have different primary outcomes, therefore the sample size for each trial was calculated using the appropriate outcome. The primary outcome for PROMOTE is WEMWBS, which has a minimum clinically important difference (MCID) of 3.0 units and a standard deviation (SD) of 11.3 units. Using these values, with 90% power and a statistical significance threshold of 0.05, the sample size required for a 2-arm comparison would be 300 participants per arm. Accounting for 40% attrition at 3-month follow-up (the primary follow-up timepoint), a total of 500 participants per arm are required. Therefore, across the three arms of the trial, 1500 participants are required.

The primary outcome for PREVENT is PHQ-9, which has an established MCID of 5.9 and SD of 5.4. Using the same power requirements as for PROMOTE, the sample size required per arm is 93 participants. Accounting for 40% attrition at 3-month follow-up, 155 participants per arm are required, producing a total of 465 participants across the three arms.

A top level cohort, comprising young adults potentially eligible for either PROMOTE or PREVENT is to be recruited. It is anticipated that within such a top level cohort, 70% will be eligible for PROMOTE and 30% for PREVENT. Given that 1500 participants are required for PROMOTE, a top level cohort of 2142 potential participants will be required. The remaining 30% of the cohort, 642 participants, exceeds the required sample size for PREVENT.

For all participants recruited within the first 2 months from start of recruitment (anticipated to be approximately 450), we will calculate loss to 3-month follow-up and should it exceed 40% (as allowed for in the sample size calculation), we will re-adjust the sample size accordingly. Note that in the event of loss to follow-up being less than 40%, the sample size will not be reduced.

Full details of the sample size calculations, including references for the parameters used, are set out in Protocol v.1.3.

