10.1.2 Sample size calculation for ECoWeB-PREVENT

The sample size calculation for ECoWeB-PREVENT is based on the primary outcome, PHQ-9 score, which has an established and published MCID of 2.59 and SD of 5.4 (Löwe et al., 2004). Prior to accounting for attrition, 93 participants per arm are required. Accounting for attrition of 40% at 3-month follow-up, this requires 155 participants per arm; with 3 trial arms this gives a total sample target for the ECoWeB-PREVENT trial of N=465.

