## 6. Statistical analysis

#### 6.1 Trial outcomes

All trial outcomes will be collected for both PROMOTE and PREVENT; the only difference between the trials in terms of outcome variables is in the choice of primary outcome measures. For PROMOTE, the primary outcome measure is WEMWBS, whereas for PREVENT the primary outcome measure is PHQ-9.

Outcomes for PROMOTE and PREVENT include

- 1. WEMWBS (primary outcome measure for PROMOTE)
- 2. PHQ-9 (primary outcome measure for PREVENT)
- 3. WSAS
- 4. GAD-7
- 5. EQ5D-3L
- 6. ADSUS-adapted (health economic evaluation)
- 7. MINI-IPIP-N

Full details of these outcomes are set out in the Data Management Plan (more specifically Data Dictionary appendix), including the following items.

- 1. Full name of outcome measure
- 2. Abbreviation
- 3. Description of what is being measured
- 4. Type of measure: screening, outcome, mechanistic
- 5. Directionality (high scores indicate more positive or negative outcome)
- 6. Number of items
- 7. Item ranges

- 8. Overall score ranges
- 9. Subscales with number of items, item numbers, range
- 10. Item numbers for items that require reverse coding (i.e. the meaning of the item is expressed in the opposite direction from the overall scale)
- 11. Guidelines to address individual item missingness
- 12. MCID (if available)
- 13. Metric used for calculation (e.g. mean, total, percentage, algorithm)

All outcomes are questionnaire based continuous measures. The primary follow-up timepoint is 3 months, therefore the primary outcome for PROMOTE is WEMWBS at 3-month follow-up, for PREVENT the primary outcome is PHQ-9 at 3-month follow-up.

For ease of interpretation, all continuous outcomes will be reported using the directionality of higher scores indicating a more positive outcome. Therefore, some scales will be reversed by comparison to their standard usage (see the Data Management Plan for more details on outcome variables and their scoring procedures).

For each follow-up timepoint, there will be an initial email sent to the participant to request outcome data, followed by a reminder after 7 days. The link to submit outcome data will expire after 2 weeks following the reminder, resulting in a time window for data collection of just under 3 weeks. It is possible that some data collection may occur outside the time window, e.g. data collected by telephone.

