#### 6.1.1 Derived variables

For the primary outcome in each trial we will create binary outcomes to indicate whether the participant (i) had an improvement  $\geq$ MCID from baseline and (ii) had a deterioration  $\geq$ MCID from baseline. These outcomes will be included in the inferential analyses for the ITT population using observed data only.

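### SAP 3.4 prints a PHQ-9 MCID of 5.9 where the protocol has 2.59; only 2.59 gives the stated 93 per arm, and SAP 6.1.1 relies on an MCID without giving its value

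*SAP*

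**What the plan says.** SAP section 3.4 gives the PREVENT inputs: "The primary outcome for PREVENT is PHQ-9, which has an established MCID of 5.9 and SD of 5.4". It applies the power requirements used for PROMOTE (90% power, threshold 0.05) and concludes that "the sample size required per arm is 93 participants", rising to 155 per arm after 40% attrition and 465 over three arms. It closes with a cross-reference: "Full details of the sample size calculations, including references for the parameters used, are set out in Protocol v.1.3".

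Protocol section 10.1.2 gives PHQ-9 an "established and published MCID of 2.59 and SD of 5.4" and reaches the same 93, 155 and 465. Protocol section 10.1 specifies a two-sided test, 90% power, alpha 0.05 and 40% attrition, with no multiplicity adjustment.

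SAP section 6.1.1 then uses an MCID as a cut-off: "For the primary outcome in each trial we will create binary outcomes to indicate whether the participant" improved, or deteriorated, by at least the MCID from baseline. Both outcomes go into the inferential analyses on observed ITT data. No value is printed there. SAP section 6.1 says that details of each outcome, including its MCID where there is one, are held in the data dictionary appendix of the Data Management Plan. SAP section 1.4 adds: "This SAP is not intended to be a standalone document and should be used in conjunction with the trial protocol".

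**The concern.** The two current documents give different values for the same parameter and the same answer from it. Both cannot be right, and a reader who tries to reproduce the SAP's sample size from the SAP's own inputs will fail.

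The second problem follows from the first. Section 6.1.1 needs an MCID, and 5.9 is the only PHQ-9 MCID printed anywhere in the SAP. Protocol section 10.3 also says that the SAP's details take precedence over the protocol's summary of the statistical analysis, and that summary does not mention these MCID-based outcomes. A programmer coding 6.1.1 could reasonably look to SAP 3.4. Improvement and deterioration in PREVENT would then be judged against a change more than twice the difference on which the trial was sized (5.9 / 2.59 = 2.28). Fewer participants would be counted as worsening in the higher-risk trial.

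**Working it through.** **Inputs.** SD 5.4 (both documents). MCID 5.9 (SAP 3.4) or 2.59 (Protocol 10.1.2). Two-sided alpha 0.05, power 0.90, attrition 40% (Protocol 10.1). Equal allocation (SAP 3.1).

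**Formula.** Normal approximation: n per arm = 2(z₀.₉₇₅ + z₀.₉₀)² / d², with d = MCID/SD and (1.960 + 1.282)² = 10.507. The two-sample t-test solution adds about one participant per arm.

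**Check of method on PROMOTE.** d = 3.0/11.3 gives 299.1 by t-test, against a stated 300. The method matches the plan's.

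**PREVENT with the protocol's MCID.** d = 2.59/5.4 = 0.480.
- Normal: 2 × 10.507 / 0.480² = 91.4, so 92.
- t-test: 92.3, so 93. Power at 93 per arm is 90.2%.
- Attrition: 93/0.6 = 155 per arm; 155 × 3 = 465.

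All three stated figures reproduce.

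**PREVENT with the SAP's MCID.** d = 5.9/5.4 = 1.093.
- Normal: 2 × 10.507 / 1.093² = 17.6, so 18.
- t-test: 18.6, so 19.
- After attrition: 18/0.6 = 30 or 19/0.6 = 31.7, so 30 or 32 per arm (90 or 96 in total).
- Power at 93 per arm would exceed 99.99%.

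No plausible variant at 5.9 comes near 93:

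| Variant at MCID 5.9 | n per arm, normal (t-test) |
|---|---|
| Two-sided, 90% power | 18 (19) |
| One-sided, 90% power | 15 (16) |
| Two-sided, 80% power | 14 (15) |
| One-sided, 80% power | 11 (12) |
| Two-sided, 90% power, alpha/3 | 23 |

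**Working back from 93 per arm (t-test).** At SD 5.4 the detectable difference is 2.58. For 5.9 to require 93 per arm, the SD would have to be about 12.3.

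**What the wrong value would do in 6.1.1.** PHQ-9 items score 0 to 3 in whole numbers, so with complete totals a 2.59 cut-off means 3 or more points and a 5.9 cut-off means 6 or more. To show scale only, assume mean-zero normal change scores, 30% of the revised target of 3599 in PREVENT and 40% attrition: 0.30 × 3599 / 3 × 0.60 = 215.9 analysed per arm. In one direction:

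| Assumed SD of change | Reach 2.59 | Reach 5.9 |
|---|---|---|
| 5.4 | 0.316 × 215.9 = 68 | 0.137 × 215.9 = 30 |
| 4 | 0.259 × 215.9 = 56 | 0.070 × 215.9 = 15 |

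Neither SD is established: the documents do not say whether 5.4 is the SD of change, and 4 is an assumption chosen to show a range.

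**The case against.** The strongest reply is that this is a misprint with no effect on the design. The figures 93, 155 and 465 agree in both documents. Recruitment is driven by PROMOTE, and the 642 expected for PREVENT at the initial cohort size already exceeded 465. SAP 3.4 sends the reader to the protocol for the parameters. All of that stands. The precedence statement in Protocol 10.3 concerns the analysis summary, so it does not make 5.9 the governing sample-size input.

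On 6.1.1, the SAP does name a home for the MCID, and it is not section 3.4. The data dictionary may already hold the right value, or a deliberately different one for within-person change. This also stands: nobody working from the protocol and SAP alone can say that the threshold is wrong, only that it is not stated there and that the one figure the SAP does print is incorrect.

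The outcomes are supplementary, and the PHQ-9 table shell (Table A.5) has no row for them. They are nonetheless listed for inferential analysis.

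The participant counts are soft. Using half-point boundaries for an integer scale (2.5 and 5.5) gives about 69 versus 33 per arm at SD 5.4, and 57 versus 18 at SD 4. Because current and past depression are excluded, low baseline scores are plausible, and a participant who starts below 6 cannot improve by 6. The symmetric picture is therefore doubtful for improvement. These points change the illustration, but they do not touch the mismatch or the need for a stated threshold.

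**Conclusion.** The concern holds. The PHQ-9 MCID of 5.9 in SAP 3.4 is inconsistent with the SAP's own 93 per arm (it implies 18 to 19) and with the protocol's 2.59, which reproduces every stated figure. This rests only on inputs printed in the documents. The planned sample size and the primary analysis are not affected.

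The consequence for 6.1.1 is conditional on an analyst taking the threshold from SAP 3.4 rather than from the protocol or the data dictionary. In that case the PHQ-9 cut-off doubles from 3 to 6 points on complete totals, and the number classified per direction falls to roughly a quarter to a half of what it would be (30/68 = 0.44 at SD 5.4; 15/56 = 0.27 at SD 4) under the assumptions above. It should be fixed, but it does not threaten the trial's main conclusion.

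**What to change.** 1. In SAP 3.4, change the PHQ-9 MCID from 5.9 to 2.59.
2. In SAP 6.1.1, state the thresholds as numbers: WEMWBS 3.0; PHQ-9 2.59, meaning 3 or more points when totals are whole numbers.
3. Check that the MCID entries in the data dictionary agree. If it intentionally holds a different value for within-person change, state that value in 6.1.1 and give the reason.

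The cost is one figure, one sentence and a check of the dictionary entries, with no extra participants or data. It should be done before the data are analysed: SAP 1.7 treats revisions made after scrutiny of the data and unblinded interpretation as post hoc and needing strong justification, and a responder threshold settled that late could look chosen with the results in hand.

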10.3 Statistical analysis plan

A detailed statistical analysis plan (SAP) is to be produced; the main points of the statistical analysis are summarised here – for full details see project SAP whose details supercede this. The statistical analysis for each trial will follow the same broad guidelines; any adaptations for each trial individually we reported

in the detailed SAP. The SAP will be approved by the TSC prior to end of participant recruitment. Any amendments to the TSC will be documented and approved by the TSC on an ongoing basis.

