10.3.2 Primary analysis

The primary outcomes (WEMWBS (ECoWeB-PROMOTE); PHQ-9 (ECoWeB-PREVENT) and secondary outcomes will be compared at 3-month follow-up. The primary and secondary continuous outcomes will be reported descriptively (mean and standard deviation (SD)) and inferential comparisons will be reported between the three treatment contrasts ((1) usual practice plus personalised digital self-help EC vs. usual practice alone; (2) usual practice plus non-personalised automated digital CBT self-help vs. usual practice alone; (3) usual practice plus personalised digital self-help EC vs. usual practice alone; (3) usual practice plus personalised digital self-help EC vs. usual practice plus non-personalised automated digital CBT self-help) using linear modelling. All analyses will be based on an intention to treat principle (i.e. according to original allocation irrespective of intervention adherence) and will include participants with complete outcome data at 3-month follow-up, and will adjust for baseline outcome score (where relevant) and minimisation variables (age, gender, country). Furthermore, we will adjust for any baseline participant characteristics that are substantively unbalanced at baseline (defined as a difference ≥ 10 percentage points across categories for a categorical variable, or a difference in means >1 SD for continuous variables), and if the characteristic is thought to be predictive of outcome. Binary secondary outcomes (occurrence of major depressive disorder; generalized anxiety disorder) will be reported as proportions and analysed used logistic regression.

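### SAP 3.4 misstates the PHQ-9 MCID as 5.9 (the sample size used 2.59) while SAP 6.1.1 uses an unnumbered MCID as a cut-off; protocol and SAP also conflict on MDD and GAD occurrence

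*SAP*

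**What the plan says.** **PHQ-9 MCID.** SAP 3.4 reads: "The primary outcome for PREVENT is PHQ-9, which has an established MCID of 5.9 and SD of 5.4". It continues: "Using the same power requirements as for PROMOTE, the sample size required per arm is 93 participants". Protocol 10.1.2 describes the PHQ-9 as a measure "which has an established and published MCID of 2.59 and SD of 5.4". Both documents then inflate 93 for 40% attrition to 155 per arm, or 465 across three arms. SAP 3.4 refers the reader to Protocol v1.3 for the full calculation and the sources of its parameters.

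**Where the MCID is used again.** SAP 6.1.1 states: "For the primary outcome in each trial we will create binary outcomes to indicate whether the participant" improved, or deteriorated, by at least the MCID from baseline. It adds: "These outcomes will be included in the inferential analyses for the ITT population using observed data only". No number is given there. SAP 6.1 says that outcome details, including an MCID where available, are in the Data Dictionary appendix of the Data Management Plan. SAP 6.1 also says that scales will be reversed where needed so that higher scores are better.

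**Binary outcomes.** Protocol 10.3.2 states: "Binary secondary outcomes (occurrence of major depressive disorder; generalized anxiety disorder) will be reported as proportions and analysed used logistic regression". SAP 6.1 lists seven measures, none of them MDD or GAD occurrence, and says: "All outcomes are questionnaire based continuous measures". Protocol 10.3 says of its own analysis summary: "for full details see project SAP whose details supercede this".

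**The concern.** The two documents give different MCIDs with the same SD and the same sample size, so one MCID must be wrong. A slip confined to a sample-size paragraph would be cosmetic. Here the term is used again, without a value, to classify each PREVENT participant as improved or worsened, and those classifications are tested between arms. An analyst who looks in the SAP for the PHQ-9 MCID finds only 5.9.

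The second matter is also a disagreement between the documents. The protocol prespecifies two diagnostic-type secondary outcomes, and the SAP neither lists them nor says that they were dropped. Neither document says how they are derived. If this stays open until allocation is known, whether to analyse them, and at what GAD-7 cut-off, becomes a choice that the results could influence.

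**Working it through.** **Inputs.** SD 5.4 (both documents); two-sided alpha 0.05, 90% power, 40% attrition and no multiplicity adjustment (Protocol 10.1); 1:1 within each pairwise contrast (SAP 3.1). MCID 2.59 (Protocol 10.1.2) or 5.9 (SAP 3.4).

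**Formula.** n per arm = 2 × SD² × (z₀.₉₇₅ + z₀.₉₀)² / MCID², then a small increase for the t distribution. The constant part is 2 × 29.16 × (1.960 + 1.2816)² ≈ 612.8.

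**Reproducing the stated figure with 2.59.** 612.8 / 6.708 = 91.4, so 92 by the normal approximation. The two-sample t solution is 92.3, so 93. Then 93 / 0.6 = 155, and 155 × 3 = 465. All three stated numbers are matched.

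**The same with 5.9.** 612.8 / 34.81 = 17.6, so 18. The t solution is 18.6, so 19. Then 19 / 0.6 = 31.7, so 32 per arm, and 32 × 3 = 96.

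**Could other settings rescue 5.9?** One-sided testing, 80% power, and alpha of 0.025, 0.0167 or 0.01 were tried; none gives more than 25 per arm. Reaching 93 would need an SD of about 12.4. At 93 per arm, the difference detectable with 90% power is 2.57.

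**Effect on the 6.1.1 cut-off.** The PHQ-9 has nine items scored 0 to 3, so totals are whole numbers from 0 to 27. A change of at least 2.59 means 3 points or more; a change of at least 5.9 means 6 points or more. The score cannot fall below 0, so a participant with baseline b can improve by at most b. At 6 points, anyone with b of 5 or less cannot be classed as improved; at 3 points this holds only for b of 2 or less. Protocol 6.2 excludes current depression, so low baseline scores are to be expected. The documents give no baseline PHQ-9 distribution, so the share of participants affected cannot be calculated from them. PROMOTE has no such problem: both documents give 3.0 for the WEMWBS.

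**Binary outcomes, side by side.**

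| | Protocol | SAP |
|---|---|---|
| MDD and GAD occurrence named | Yes (10.3.2) | No (6.1) |
| Outcome types | Continuous and binary (10.3.2) | All continuous (6.1), yet 6.1.1 creates binary ones |
| Logistic regression for binary outcomes | Yes (10.3.2) | Yes, in general terms (6.3) |
| Derivation of MDD or GAD occurrence | Not given | Not given |

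The data exist. Protocol 3.7 schedules LIDAS at 3 months (last 3 months) and 12 months (last 12 months), and GAD-7 at both visits. Participants followed up by telephone give the primary measures only (Protocol 7 and 7.7), so they would lack both.

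**The case against.** The strongest reply on the MCID is that 5.9 is plainly a slip for 2.59: the sample sizes identify the right value and SAP 3.4 defers to the protocol. That is correct for the sample size. A reader might infer that PREVENT was wrongly sized; the arithmetic rules this out. A reader might also infer that the 6.1.1 cut-off is definitely wrong. The documents do not show that, because the Data Dictionary may state the right value. What stands is that the SAP's own text is inconsistent and does not settle the cut-off.

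It is also fair to say that reproducing 93 shows which value sized a between-group comparison, not that 3 points is the best threshold for change in one person. But 6.1.1 chose the MCID as its threshold, and 2.59 is the value that the protocol calls established and published.

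On the binary outcomes, a tempting stronger reading is that, because the SAP supersedes the protocol, neither analysis would be done. The documents do not support this. SAP 1.4 says the SAP must be read together with the protocol, SAP 6.3 keeps logistic regression for binary outcomes, and silence is not clearly a superseding detail. The absence of a table shell proves little, since the 6.1.1 outcomes have none either. Nor does the absence of an entry in SAP Table 4, which logs changes between SAP versions and would be silent if version 1.0 never listed these outcomes. Protocol 10.3.2 may itself be the outlier: the hypotheses in Protocol 3.1 and the 12-month endpoint in 3.5 do not name MDD or GAD occurrence, and Protocol 3.7 labels LIDAS as screening for past depression. So the conflict is real, but the documents do not say which side was intended.

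**Conclusion.** The PHQ-9 MCID in SAP 3.4 is wrong as written. With the stated SD, power and alpha, 2.59 gives 93, 155 and 465; 5.9 gives about 19, 32 and 96. The sample size and the primary analysis need no change. The exposure is limited to PREVENT's improvement and deterioration outcomes, where the printed value implies a cut-off of 6 points instead of 3 and excludes everyone with a baseline of 5 or less from counting as improved. This rests on whole-number scoring and on the SAP's text alone, with the Data Dictionary unseen. Any percentage of participants reclassified would depend on an assumed baseline distribution and on how screening shapes it, so none is offered.

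The secondary point is an unresolved conflict over whether MDD and GAD occurrence are outcomes. It is not a demonstrated loss of two analyses. Both matters are worth correcting, and neither threatens the main result.

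**What to change.** 1. **SAP 3.4:** change 5.9 to 2.59.
2. **SAP 6.1.1:** print the cut-offs as numbers: a PHQ-9 change of 3 points or more and a WEMWBS change of 3 points or more. Give the direction explicitly, because SAP 6.1 reverses scales: deterioration on the PHQ-9 is a rise on standard scoring and a fall on the reversed scale. Check both against the Data Dictionary and correct whichever is wrong.
3. **SAP 6.1, before unblinding, one of two routes:**
   - List MDD and GAD occurrence as binary secondary outcomes and amend the sentence that calls all outcomes continuous. Take MDD from LIDAS at 3 and 12 months. Take GAD from the GAD-7 with a cut-off stated in advance (the documents give none), adjusting for baseline GAD-7, since the exclusion criteria in Protocol 6.2 do not name anxiety. Use the logistic regression in SAP 6.3, report n/N (%) by arm, and state how many telephone completers lack these data.
   - Or record in SAP Table 4 that they are not outcomes, and why, and align Protocol 10.3.2.

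**Cost.** SAP wording and, on the first route, one table; no new data collection. That route brings 2 outcomes × 3 contrasts × 2 visits × 2 trials = 24 unadjusted secondary contrasts, all within what the protocol already plans, and events may be sparse in PREVENT. Made after unblinded interpretation, these changes would count as post hoc under SAP 1.7.
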